3.1 Inclusion Criteria

3.1.1 Advanced metastatic, progressing carcinoid or pancreatic islet cell cancers

3.1.2 No prior chemotherapy or anti-angiogenic therapy. One prior mTOR inhibitor is allowed. Patients may have received one line of prior therapy with somatostatin analogue, locoregional therapy. Continuation of concurrent somatostatin analogue is allowed. Patients will be maintained on somatostatin analogue for the duration of their treatment.

3.1.3 Age \geq 18 years.

3.1.4 Life expectancy of at least 12 weeks (3 months).

3.1.5 Subjects must be able to understand and be willing to sign the written informed consent form. A signed informed consent form must be appropriately obtained prior to the conduct of any trial-specific procedure.

3.1.6 All acute toxic effects of any prior treatment have resolved to NCI-CTCAE v4.0 Grade 1 or less at the time of signing the Informed Consent Form (ICF). Exceptions to this include alopecia.

3.1.7 Adequate bone marrow, renal and liver function as assessed by the following laboratory requirements:

- Total bilirubin \leq 1.5 x the upper limits of normal (ULN)
- Alanine aminotransferase (ALT) and aspartate amino-transferase (AST) \leq 2.5 x ULN (\leq 5 x ULN for subjects with liver involvement of their cancer)
- Alkaline phosphatase limit \leq 2.5 x ULN (\leq 5 x ULN for subjects with liver involvement of their cancer)
- Lipase \leq 1.5 x the ULN
- Amylase \leq 1.5 x the ULN
- Serum creatinine \leq 1.5 x the ULN
- International normalized ratio (INR)/ Partial thromboplastin time (PTT) $<$ 1.5 x ULN. (Subjects who are treated with an agent such as warfarin or heparin will be allowed to participate provided that no prior evidence of underlying abnormality in coagulation parameters exists. Close monitoring (day 5 of cycle 1 and day 1 of each cycle) is mandatory) will be performed until INR/PTT is stable based on a measurement that is pre-dose as defined by the local standard of care.
)
- Platelet count \geq 100,000 /mm³, hemoglobin (Hb) \geq 9 g/dL, absolute neutrophil count (ANC) \geq 1,500/mm³. Blood transfusion to meet the inclusion criteria will not be allowed.

-
- 3.1.8 Glomerular filtration rate (GFR) \geq 30 ml/min/1.73 m² according to the Modified Diet in Renal Disease (MDRD) abbreviated formula.

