- 3.1.39 Uncontrolled, intercurrent illness including, but not limited to, ongoing or active infection, symptomatic congestive heart failure, unstable angina pectoris, cardiac arrhythmia, or psychiatric illness/social situations that would limit compliance with study requirements.
- 3.1.40 Excluded therapies and medications, previous and concomitant
- Concurrent anti-cancer therapy (chemotherapy, radiation therapy, surgery, immunotherapy, biologic therapy, or tumor embolization) other than study treatment (regorafenib).
 - Prior use of regorafenib.
 - Concurrent use of chemotherapy, radiotherapy or another investigational drug or device therapy (i.e., outside of study treatment) during, or within 4 weeks of trial entry (signing of the informed consent form)
 - Major surgical procedure, open biopsy, or significant traumatic injury within 28 days before start of study medication.
 - Use of any herbal remedy (e.g. St. John's wort [*Hypericum perforatum*])

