6.1.2 Disease Parameters (RECIST 1.1)

Measurable disease. Measurable lesions are defined as those that can be accurately measured in at least one dimension (longest diameter to be recorded) as ≥ 20 mm with conventional techniques (CT, MRI, x-ray) or as ≥ 10 mm with spiral CT scan. All tumor measurements must be recorded in millimeters (or decimal fractions of centimeters).

Note: Previously irradiated lesions are non-measurable except in cases of documented progression of the lesion since the completion of radiation therapy.

Non-measurable disease. All other lesions (or sites of disease), including small lesions (longest diameter < 20 mm with conventional techniques or < 10 mm using spiral CT scan), are considered non-measurable disease. Bone lesions, leptomeningeal disease, ascites, pleural/pericardial effusions, lymphangitis cutis/pulmonis, inflammatory breast disease, abdominal masses (not followed by CT or MRI), and cystic lesions are all non-measurable.

Target lesions. All measurable lesions up to a maximum of 2 lesions per organ and 5 lesions in total, representative of all involved organs, should be identified as **target lesions** and recorded and measured at baseline. Target lesions should be selected on the basis of their size (lesions with the longest diameter) and their suitability for accurate repeated measurements (either by imaging techniques or clinically). A sum of the longest diameter (LD) for all

target lesions will be calculated and reported as the baseline sum LD. The baseline sum LD will be used as reference by which to characterize the objective tumor response.

Malignant lymph nodes. To be considered pathologically enlarged and measurable, a lymph node must be >15 mm in short axis when assessed by CT scan (CT scan slice thickness recommended to be no greater than 5 mm). At baseline and in follow-up, only the short axis will be measured and followed.

Non-target lesions. All other lesions (or sites of disease) including any measurable lesions over and above the 5 target lesions should be identified as **non-target lesions** and should also be recorded at baseline. Measurements of these lesions are not required, but the presence or absence of each should be noted throughout follow-up.

6.1.3 **Methods for Evaluation of Measurable Disease**

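### Embolised or ablated lesions may serve as target lesions, because the measurability note in 6.1.2 covers only irradiated lesions and no look-back in 3.1.40 names embolisation or ablation

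*Combined protocol and SAP*

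**What the plan says.** - **Measurability (6.1.2).** The only rule that looks at prior local treatment is: "Previously irradiated lesions are non-measurable except in cases of documented progression of the lesion since the completion of radiation therapy".
- **Target selection (6.1.2).** "Target lesions should be selected on the basis of their size (lesions with the longest diameter) and their suitability for accurate repeated measurements". There is a cap of two per organ and five in total, and targets are to represent all involved organs. Prior local treatment is not a selection criterion.
- **Prior therapy (3.1.2).** "Patients may have received one line of prior therapy with somatostatin analogue, locoregional therapy". No interval is given.
- **Disease status (3.1.1).** "Advanced metastatic, progressing carcinoid or pancreatic islet cell cancers". There is no time window, no criterion for progression and no link to a particular lesion.
- **Excluded therapies (3.1.40).** Embolisation appears once, in the list of barred concurrent treatments: "Concurrent anti-cancer therapy (chemotherapy, radiation therapy, surgery, immunotherapy, biologic therapy, or tumor embolization) other than study treatment (regorafenib". The 4-week look-back covers chemotherapy and "radiotherapy or another investigational drug or device therapy (i.e., outside of study treatment) during, or within 4 weeks of trial entry". A separate 28-day rule covers major surgery, open biopsy and significant trauma.
- **On-study radiation (4.3).** Palliative radiation is allowed only if target lesions lie outside the field.

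**The concern.** In two places the protocol accepts that a locally treated lesion is a poor gauge of drug effect: it bars irradiated lesions that have not progressed since, and it keeps target lesions out of palliative radiation fields. Embolisation and ablation raise the same attribution problem, and these patients are expressly admitted, but the rule stops at radiation.

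If such a lesion is a target and is still shrinking, or being held, because of the earlier procedure, the change enters the sum of diameters as if regorafenib had caused it. That can produce a partial response, or hide growth in other targets and so support a 'yes' for 6-month PFS. Each cohort is single-arm and judged against a fixed rate, so the analysis cannot separate carry-over from drug effect.

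**Working it through.** **1. The plan's own figures.** From 10.2: 11 then 13 patients per cohort. Cohort A continues with at least 5 of 11 and succeeds with at least 14 of 24; cohort B continues with at least 7 of 11 and succeeds with at least 18 of 24. From 10.1: null and alternative rates are 40% and 65% (A), 57% and 80% (B).

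Pr(success | p) = Σ over x₁ from the continuation limit to 11 of Bin(x₁; 11, p) × Pr[Bin(13, p) ≥ c − x₁], with c = 14 (A) or 18 (B).

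| Cohort | Error at null | Stated | Power at alternative | Stated |
|---|---|---|---|---|
| A | 5.14% | 5.1% | 80.5% | 80% |
| B | 5.31% | 5.3% | 80.1% | 80% |

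The stated design reproduces, and this point disputes none of these figures.

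**2. How carry-over enters the measurement.** Take two 50 mm targets (baseline sum 100 mm), one recently embolised, and no drug effect.

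- The treated lesion shrinks 60% and the other is unchanged: 20 + 50 = 70 mm, a 30% fall. This meets the partial-response threshold in 6.1.4.1, and 6.1.5 requires no confirmation.
- The treated lesion shrinks 30% while the other grows 30%: 35 + 65 = 100 mm, no change. This is scored as stable disease.
- The opposite direction: the treated lesion first shrinks 30% and the other is stable, so the nadir is 35 + 50 = 85 mm. Progression is then a sum of 1.2 × 85 = 102 mm, reached when the other lesion is 102 − 35 = 67 mm (34% growth). Without the shrinkage the threshold is 120 mm, and the other lesion would have to reach 70 mm (40% growth). Here carry-over brings progression forward.

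**3. Effect on the false-positive rate.** Let f be the share of patients affected and q their 6-month PFS rate with an inactive drug. The cohort rate is p = (1 − f)·p₀ + f·q, put into the formula in step 1. The documents give neither f nor q; **all values below are assumptions**.

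| Cohort | f | q | p | False-positive rate |
|---|---|---|---|---|
| A | 10% | 50% | 0.90 × 0.40 + 0.10 × 0.50 = 0.410 | 6.3% |
| A | 10% | 60% | 0.90 × 0.40 + 0.10 × 0.60 = 0.420 | 7.7% |
| A | 20% | 60% | 0.80 × 0.40 + 0.20 × 0.60 = 0.440 | 11.0% |
| A | 30% | 70% | 0.70 × 0.40 + 0.30 × 0.70 = 0.490 | 23.1% |
| B | 10% | 65% | 0.90 × 0.57 + 0.10 × 0.65 = 0.578 | 6.2% |
| B | 20% | 80% | 0.80 × 0.57 + 0.20 × 0.80 = 0.616 | 12.2% |

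Regardless of f and q, a 2-point rise in the true null rate gives 7.7% (A) and 7.8% (B); a 5-point rise gives 12.9% and 13.0%.

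**The case against.** Several stronger readings are tempting, and the documents do not support them.

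- **That no washout covers local therapy.** Radiotherapy has a 4-week look-back and major surgery 28 days. Chemo- or radio-embolisation might be read into the 4-week wording, though the text does not say so. Only bland embolisation and non-surgical ablation are clearly uncovered.
- **That a patient embolised days before registration simply walks in.** Disease must be progressing (3.1.1), acute toxicity of prior treatment must have settled to Grade 1 or less (3.1.6), liver tests must be within limits (3.1.7), and the investigator may judge a patient unsuitable (3.1.35). These narrow the gap. They do not close it, because a patient can be progressing elsewhere while the treated lesion is still responding.
- **That treated lesions will be the targets because they are largest.** Nothing says they are largest, and selection also depends on repeatability and on representing all involved organs. They may be chosen; that is all the text shows.
- **That the bias runs only one way.** A lowered nadir can bring progression forward, as shown above. New lesions and unequivocal non-target progression count as progression (6.1.4), as does clinical deterioration without a scan (10.3).
- **That the error rate is 11% to 23%.** Those figures need high inputs. For cohort A, q = 70% exceeds the protocol's own alternative of 65%; for cohort B, q = 80% equals it. And f is the share with an unprogressed treated target lesion, which is smaller than the share with any prior locoregional therapy.

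It is also fair to say that 10.1 takes its null rates from a trial in a similar setting. If that trial admitted similarly pretreated patients, some carry-over is already in the 40% and 57%. The documents do not settle this.

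What remains is that no rule stops a recently embolised or ablated lesion from being a target.

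**Conclusion.** The gap is real and modest. As written, a recently embolised or ablated lesion may be measured as a target, and carry-over may be credited to regorafenib. The response rate, a secondary endpoint analysed descriptively, is most directly exposed. The 6-month PFS decision is exposed less directly, through masked growth. The net bias is likely, but not certain, to favour regorafenib.

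The size is unknown. The calculated range, from close to the stated error rates up to 23% (A) and 12% (B), rests entirely on assumed shares and carry-over, and on the null rates containing none of it already. The upper ends show sensitivity and are not estimates. This is a cheap improvement, not a defect that invalidates the design.

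**What to change.** Extend the note in 6.1.2 along these lines: *Lesions previously treated by radiation, embolisation, ablation or other locoregional therapy are non-measurable unless the lesion has documented progression since that treatment.* Because 3.1.13 already requires measurable disease, the change carries through to eligibility.

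Add a field to the baseline tumour form recording, for each lesion, any prior local treatment. Even without the rule, this would show how many patients are affected.

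This is a measurement rule. It sets no treatment interval and changes no sample size, decision boundary, error rate or power. The cost is one sentence, one form field, and a few patients whose only measurable lesions were locally treated and who are not eligible until progression of a lesion is documented. At about one patient accrued per month, that cost is not nil, but it should be small.

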6.1.4.2 Evaluation of Non-Target Lesions

Complete Response (CR): Disappearance of all non-target lesions and normalization of tumor marker level.

Incomplete Response/Stable Disease (SD): Persistence of one or more non-target lesion(s) and/or maintenance of tumor marker level above the normal limits.

Progressive Disease (PD): Appearance of one or more new lesions and/or unequivocal progression of existing non-target lesions

6.1.4.3 Evaluation of Best Overall Response

The best overall response is the best response recorded from the start of the treatment until disease progression/recurrence (taking as reference for progressive disease the smallest measurements recorded since the treatment started). The patient's best response assignment will depend on the achievement of both measurement and confirmation criteria.

Target Lesions	Non-Target Lesions	New Lesions	Overall Response	Best Response for this Category Also Requires:
CR	CR	No	CR	≥4 wks. confirmation
CR	Non-CR/Non-PD	No	PR	≥4 wks. confirmation
PR	Non-PD	No	PR	
SD	Non-PD	No	SD	documented at least once ≥4 wks. from baseline

PD	Any	Yes or No	PD	no prior SD, PR or CR
Any	PD*	Yes or No	PD	
Any	Any	Yes	PD	
* In exceptional circumstances, unequivocal progression in non-target lesions may be accepted as disease progression.				

Note: Patients with a global deterioration of health status requiring discontinuation of treatment without objective evidence of disease progression at that time should be reported as “*symptomatic deterioration*”. Every effort should be made to document the objective progression even after discontinuation of treatment.

Note: If subjects respond to treatment and are able to have their disease resected, the patient’s response will be assessed prior to the surgery.

6.1.5 **Confirmation of Response:**

Confirmation of response is not required in this trial as response is not the primary endpoint.

6.1.6 **Duration of Response**

Duration of overall response: The duration of overall response is measured from the time measurement criteria are met for CR or PR (whichever is first recorded) until the first date that recurrent or progressive disease is objectively documented (taking as reference for progressive disease the smallest measurements recorded since the treatment started).

The duration of overall CR is measured from the time measurement criteria are first met for CR until the first date that recurrent disease is objectively documented.

Duration of stable disease: Stable disease is measured from the start of the treatment until the criteria for progression are met, taking as reference the smallest measurements recorded since the treatment started.

6.1.7 **Progression-Free Survival (PFS)**

Progression-free survival (PFS) is defined as the duration of time from start of treatment to time of progression or death on study whichever comes first. Patients who go off treatment for reasons other than disease progression or death will be censored at the time of the last CT scan.

6.1.8 **Time to Treatment Failure (TTF)**

Time to treatment failure is defined as from start of treatment until time to progression, death, start of alternate therapy or development of secondary malignancy, whichever comes first.

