4.6 Duration of Follow Up

Patients will be followed with phone calls every 3 months until death after removal from treatment. Patients removed from treatment for unacceptable adverse events will be followed until resolution or stabilization of the adverse event.

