5.4 Study Calendar

Cycles will be 28 Days. Regorafenib will be taken orally Days 1-21 of each Cycle. For first cycle all labs and EKG should be done within 7 days of first receiving study drug. For the first cycle, Imaging studies should be done within 28 days of first receiving study drug.

Parameter	Pre-Treatment ⁶	Day 1 of All Cycles ¹ ²	Day 8, Day 15 And 22 of Cycle 1 and 2 only ¹²	Day 15 of all Cycles ¹ ²	One Day of Week 3 Of every other Cycle (starting with Cycle 2)	Off study	Follow-up
Informed Consent	X						
Pill Diary		X				X	
History & Physical Exam	X	X					
Weight, SWOG Performance Status, Con Meds	X	X				X	
Adverse Event/Toxicity Evaluation	X	X					
WBC (differential), Hgb, Platelets	X	X		X			
Complete Metabolic Panel, Phosphorus, Magnesium, LDH	X	X	Liver function	X			
Lipase	X	X					
Thyroid Function (TSH, T3, T4)	X	X ³					
PT/PT-INR, PTT	X	X ^{3,9}					
Urinalysis for proteinuria	X	X					
5HIAA	X	X					
Serum Chromogranin	X				X		
Octreotide scan	X				Cycle 2 only		
EKG	X	X ³					
CXR (if CT of chest not done)	X ⁷				X ⁷		
BP Monitoring		X	X				
Radiology, x-ray or Scans for disease measurement ²	X ⁸				X		X ¹⁰
Archival tumor tissue	X ⁸						
Plasma	X ⁸					X ⁸	
Urine Pregnancy Test	X ⁵	X ⁵					
Survival Follow-up							X ¹¹

- 1 If used to follow measurable disease.
- 2 Within 28 days of Cycle 1, Day 1.
- 3 As clinically indicated.
- 4 Paraffin embedded tissue must be available for review.
- 5 For women of childbearing potential
- 6 Confirm response within 4 weeks.
- 7 Not required if CT scan of the chest is done.
- 8 See section 9. For plasma two purple top tubes to the [name] lab.
- 9 Close monitoring (day 5 of cycle 1 and day 1 of each cycle) of PT/PT-INR and PTT is mandatory for patients on agents such as warfarin and heparin.
- 10 Patients that come off for reasons other than disease progression will have their standard of care scans measured via RECIST until progressive disease, to determine date of disease progression
- 11 Patients will be followed up via phone call, medical records or database search until death to determine survival time
- 12 All study visits allow a +/- 7 day window

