10.3 Data Analyses Plans

Two cohorts will be analyzed separately. The primary data analysis set will include all patients who enroll the study and start to receive regorafenib for decision making in accrual and warranting further studies. Patients who withdraw the study, are lost to follow-up, or start another therapy before the status of 6-month PFS is determined will be counted as 'no' for the primary endpoint and be included in the primary data analysis set. Patients who drop out the trial before starting regorafenib will be replaced and excluded from the primary data analysis set.

The primary endpoint, 6-month PFS rate will be summarized as a proportion of patients who are alive and progression-free among all patients in the primary data analysis set. The 95% confidence intervals of the 6-month PFS rate will be calculated using the Wilson method. We chose 6-month as the cut-off point because it would be easier to compare with the historical data. The tumor response will be evaluated by CT scans every 2 cycles starting with week 3 of cycle 2. Six-months since starting treatment are 182 days, may not be on the CT scan date. CT scans will not on the strict schedules. Additional scans may be conducted to confirm a complete or partial response. Patients whose systems deteriorate clinically will be counted as progression event without confirmation of CT scans. CT scans that are conducted within ± 14 days of the landmark Day 182 will be used to determine the 6-month PFS status if there are no other scans available to determine the status. The detailed status of 6-month PFS will be counted as follows: alive and progression-free, disease progression within 6 months, death within 6 months, and progression at 6 months unknown due to early withdrawal, toxicities, or other reasons.

A sensitivity analysis of PFS at week 24 will be conducted. The PFS rate at week 24 may provide the impact of CT scheduling on estimating the 6-month PFS rate.

In addition, progression-free survival (see definition at section 6.1.7) will be analyzed using Kaplan-Meier curves. The median PFS and 95% CIs will be calculated. The probability of 6-month PFS will be estimated from the KM curve too.

The secondary endpoints including tumor response rate and OS (see definition at section 6.1.9) will be analyzed descriptively.

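### Section 6.1.7, as written, can censor progressions and deaths that the trial follows patients to observe; this affects the Kaplan-Meier PFS and the exploratory biomarker analyses, not the primary endpoint

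*Combined protocol and SAP*

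**What the plan says.** **PFS definition (6.1.7).** PFS runs from start of treatment to "time of progression or death on study whichever comes first". The next sentence is the censoring rule: "Patients who go off treatment for reasons other than disease progression or death will be censored at the time of the last CT scan". The protocol nowhere defines 'on study' for this purpose.

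**What is collected after stopping.** Under footnote 10 of the Study Calendar (5.4), patients who come off for reasons other than progression have their "standard of care scans measured via RECIST until progressive disease, to determine date of disease progression". Footnote 11 adds: "Patients will be followed up via phone call, medical records or database search until death to determine survival time". Section 4.6 says: "Patients will be followed with phone calls every 3 months until death after removal from treatment".

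**Where the definition is used.** Section 10.3 cites 6.1.7 for the KM curve and median PFS, and also takes a 6-month probability from that curve. Section 10.5 lists PFS among the outcomes for the biomarker associations.

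**What does not use it.** The primary endpoint (6.1.10) is a yes/no status at day 182. Progression or death within 6 months is 'no', and so is unknown status. Section 10.3 likewise counts as 'no' patients who withdraw, "are lost to follow-up, or start another therapy before the status of 6-month PFS is determined". OS (6.1.9) counts death from any cause.

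**The concern.** The protocol goes to some trouble to date progression and death in patients who stop early, yet its PFS definition does not clearly let those dates count. Take a patient who stops for toxicity and has RECIST progression at day 102. That patient is 'no' in the primary analysis but, under the sentence in 6.1.7, is censored in the KM analysis of the same cohort. A patient who stops and then dies without documented progression is in the same position unless 'on study' is read to include follow-up.

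Two analysts could therefore report different KM curves, medians and KM 6-month rates from identical data. If stopping is related to prognosis, censoring at stopping also biases those figures. The KM 6-month rate will be reported alongside the primary proportion, so a discrepancy would be visible and would need explaining.

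**Working it through.** **1. The design figures do not depend on 6.1.7.** Exact two-stage binomial: sum, over stage I counts that continue, P(X1 = x) times the probability of reaching the final threshold in the remaining 13 patients.

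- Cohort A (continue if at least 5/11, success if at least 14/24; 40% v 65%): type I error 0.0514, power 0.805.
- Cohort B (continue if at least 7/11, success if at least 18/24; 57% v 80%): type I error 0.0531, power 0.801.

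These match the stated 5.1%, 5.3% and 80%. They rest on the binary endpoint, so rewording 6.1.7 leaves them unchanged.

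**2. Three ways to apply 6.1.7 to a patient who leaves without progression.**

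- (a) Censor at the last CT before leaving.
- (b) Censor at the last CT of any kind, footnote 10 scans included, and count no event after leaving.
- (c) Join 6.1.7 with footnote 10: a progression dated after leaving is an event, but a death after leaving is not on study and is censored at the last scan.

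**3. Worked examples, n = 24 (invented data).** Scans fall in week 3 of cycles 2, 4 and 6, with midpoints at days 46, 102 and 158.

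*Three leavers after the day-46 scan.*
- Cohort A: 3, 2 and 2 progressions at the three scans, 14 patients progression-free. Reading (a): (21/24)(16/18)(14/16) = 68.1%. If k of the leavers progress at day 102 and are counted: (17 - k)/24 = 70.8%, 66.7%, 62.5%, 58.3% for k = 0 to 3.
- Cohort B: 2, 2 and 1 progressions, 16 progression-free. Reading (a): (22/24)(17/19)(16/17) = 77.2%. Counted: (19 - k)/24 = 79.2%, 75.0%, 70.8%, 66.7%.

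*One death off treatment at day 130 after a clean day-102 scan.*
- Cohort A: censored (21/24)(19/21)(16/18) = 70.4%; counted 16/24 = 66.7%.
- Cohort B: censored (22/24)(20/22)(18/19) = 78.9%; counted 18/24 = 75.0%.

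**4. Average error in the KM 6-month rate.** Assumptions, none of them from the documents except the scan weeks and the 40%, 65% and 80% rates used for S:

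- event hazard on treatment l = -ln(S)/182, with S = 0.40, 0.65 or 0.80;
- leaving hazard d = -ln(1 - p)/182, with p = 0.10 or 0.30;
- hazard h × l after leaving, with h = 0.5, 1, 1.5 or 3;
- 10% of events are deaths without documented progression; all others are detected at the next scan.

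Error = KM at day 182 minus the share with no documented event by day 182. That benchmark exceeds the share truly event-free because of scan delay (about 45% v 40% at S = 0.40, h = 1). The delay has nothing to do with 6.1.7.

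Reading (a), points, p = 0.10 / 0.30:

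| S | h = 0.5 | h = 1 | h = 1.5 | h = 3 |
|---|---|---|---|---|
| 0.40 | -1.0 / -3.2 | -0.1 / -0.2 | +0.6 / +2.0 | +1.9 / +6.1 |
| 0.65 | -0.7 / -2.1 | 0.0 / -0.2 | +0.5 / +1.6 | +1.8 / +5.6 |
| 0.80 | -0.4 / -1.3 | 0.0 / -0.1 | +0.3 / +1.0 | +1.3 / +3.9 |

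Reading (b): +0.6 to +12.7, positive in every cell (+0.6 to +5.2 at h = 0.5; +1.0 to +7.7 at h = 1).

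Reading (c): +0.05 to +0.96.

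For scale, one standard error at n = 24, sqrt(q(1 - q)/24), is 10.0, 9.7 and 8.2 points at 40%, 65% and 80%.

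**5. The median.** A closed form with censoring at the leaving date and no scan grid gives the order of size. With time in months, the event-free share is exp(-(l + d)t) + d·exp(-h·l·t)·(1 - exp(-kt))/k, where k = l + d - h·l. For S = 0.65, p = 0.30, h = 3: l = 0.0718, d = 0.0594, k = -0.0841, giving 0.455 + 0.127 = 58.2% at 6 months, against a KM value of 65%. The median is 7.4 months against a KM value of 9.7. For S = 0.80 with the same p and h, it is 12.5 against 18.6 months. These are the unfavourable end of the assumed range; at h = 1 there is no difference.

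**The case against.** The best defence is reading (c). A patient with a RECIST progression date under footnote 10 meets the first sentence of 6.1.7, so the censoring sentence would govern only patients with no event. Censoring someone at the very scan that shows progression, as reading (b) does, is hardly what the authors intended. This is a plausible reading, and it removes most of the progression problem. But 6.1.7 does not say it, and its second sentence says the opposite for anyone who stops for another reason. It also leaves deaths after stopping open, because 'on study' stays undefined.

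Other fair points stand:

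- The note in 6.1.4.3, "Every effort should be made to document the objective progression even after discontinuation of treatment", concerns symptomatic deterioration, and 10.3 already counts clinical deterioration as progression. It adds little.
- Time to treatment failure counts "start of alternate therapy or development of secondary malignancy, whichever comes first" and the binary endpoint treats new therapy as failure, while 6.1.7 is silent. These are different endpoints, so different handling is not a contradiction. A rule for new therapy in the KM analysis would be a useful clarification, not the repair of an error.
- Some gap between the KM rate and the binary rate is by design, since the binary endpoint counts unknown status as failure. What is not by design is a dated event counting in one and being censored in the other.
- Every magnitude rests on assumed leaving rates and hazards.

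A reader might infer that the bias always flatters regorafenib. The documents do not support that: under reading (a) it is upward if leavers do worse, downward if they do better, and about zero if leaving is unrelated to prognosis. Only reading (b) is upward throughout.

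**Conclusion.** The point holds as a minor one. Section 6.1.7 conflicts with footnotes 10 and 11 and with section 4.6, and 'on study' is undefined. The KM curve, median and KM 6-month probability, and the PFS used in the biomarker work (10.5), can therefore discard events the trial observes.

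Under the stated assumptions the KM 6-month error is about -3 to +6 points under reading (a), about +0.6 to +13 under (b), and at most about 1 under (c). Readings (a) and (c) stay within one standard error at n = 24; the extreme of (b) does not (12.7 against 10.0).

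A reader might infer that the go/no-go decisions are compromised. They are not: the binary 6-month endpoint has its own event and missing-status rules, so the stage I and final rules, type I error and power stand, as does OS.

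**What to change.** In 6.1.7, define PFS as time from first dose to the first documented progression, on or off treatment and including footnote 10 scans, or death from any cause. Censor at the last adequate tumour assessment only when neither is observed. Delete 'on study'. Cross-refer to 10.3 so that clinical deterioration is handled the same way in the KM analysis. Keep the version censored at treatment stop as a sensitivity analysis. Optionally, state how the KM analysis treats new anticancer therapy.

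The cost is a few sentences. The data are already collected under footnotes 10 and 11, and neither sample size nor decision rules change. The downsides are that KM figures may be less favourable, that off-treatment scans are unscheduled standard of care and so date progression less regularly, and that events in patients who withdraw or are lost stay unobserved. If half of the leavers were lost (an assumption), an error of 0.2 to 2.6 points would remain at h = 1.5 to 3.
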